Osteoporosis is a global health concern. According to the National Institutes of Health, approximately 10 million Americans have osteoporosis. Typically, an individual is not aware of the disease until an unexpected fracture of the leg, hip, or spine occurs. It is estimated that at least one-half of adult women and 1 in 5 adult men over the age of 50 will sustain one or more vertebral, hip or other fractures in their lifetime. The annual acute costs and subsequent costs of care related to treating osteoporotic-related injuries are estimated to be over \$14 billion. Osteopenia, a condition of around 34 million more Americans, is marked by a loss in bone mass. Frequently, osteopenia serves as "an early warning" that bone loss has started but progression can be slowed or halted by changes in life style and/or use of preventive measures or medications (Office of the Surgeon General 2004; Wright 2014).

In general, bone health can easily be maintained throughout life. Getting sufficient calcium from the diet throughout life helps to build and maintain strong bones. Since vitamin D upregulates calcium receptors and aids in calcium utilization by the body, eating foods that are rich in this vitamin and getting sufficient exposure to sunlight to aid the conversion to the active form, complement intake of dietary calcium. Finally, including regular weight-bearing exercise adds "muscle" to one's bone-health regimen.

If these actions are not sufficient to maintain bone health, several medicines are known to slow bone loss and treat osteoporosis when administered together with calcium and vitamin D. Strontium salt is one such medication. The strontium salt that is currently most widely used to treat osteoporosis is PROTOS® (strontium ranelate). Clinical studies in adults with osteoporosis have demonstrated that PROTOS reduces the incidence of fractures (both vertebral and non-vertebral) and increases bone mass and bone mineral density (Reginster 2012; Deeks 2010; Slosman 1994). Strontium salts have been safely administered to both normal subjects and subjects with osteoporosis at a daily dose as high as 2 g and for dosing periods as long as three years.

Stratum $Plus^{TM}$, is a highly pure form of strontium L-lactate (the strontium salt of L-lactic acid). Stratum Plus is manufactured in compliance with current Good Manufacturing Practices. The product has been thoroughly tested and meets rigorous purity specifications. It is free from contamination by D-lactic acid and trace metals known to harm human health. Unlike strontium renalate (and other related strontium salts), no clinical trials have been conducted with Stratum Plus. Thus, this study will be conducted to obtain pharmacokinetic (PK) information following acute oral intakes of three doses of Stratum Plus in healthy adults.

3. Objectives

The objective of this clinical trial is to obtain PK information following acute oral intakes of three doses of Stratum Plus in healthy adults.

4. Study Sample Population

Subjects will be healthy men and women 18-65 years of age, inclusive, with a body mass index (BMI) 18.0 to 31.9 kg/m². Subjects must also exhibit a body weight >60 kg, inclusionary.

5. Study Design and Procedures

5.1 Study Product

- Low dose (170 mg Sr) strontium *L*-lactate
- Medium dose (340 mg Sr) strontium L -lactate
- High dose (680 mg Sr) strontium L -lactate

The study product will be provided as a dry powder and will be diluted in distilled water for consumption.

5.2 Study Design

This is an unblinded, crossover, sequential three dose study (Figure 1). The study will include one screening visit (Visit 1; day -7) and three test visits (Visits 2, 3, and 4; days 0, 7, and 14) with at least a 6-d washout between test visits.

[figure not shown]

Figure 1.

At Visit 1 (day -7), subjects will provide informed consent and undergo screening assessments including evaluations of medical history, prior/current medication/ supplement use, inclusion and exclusion criteria, height, body weight, BMI, vital signs, and Vein Access Scale (Appendix 2). A fasting capillary blood glucose will be assessed to establish each subject's fasting level and an in-clinic urine pregnancy test (all women <60 years of age) will also be obtained. Additionally, a fasting (10-14 h) blood sample will be collected for a chemistry profile and hematology panel. Study instructions will also be provided [fasting compliance (10-14 h, water only) and avoidance of alcohol 3 d

prior to test visits (Visits 2, 3, and 4; days 0, 7, and 14]. Subjects will then be dispensed a 24-h Diet Record (Appendix 3) with instructions to record intake the day prior to Visit 2 (day 0).

At Visit 2 (day 0), subjects will arrive at the clinic fasted (10-14 h, water only, anchored to the t = -0.25 h blood draw) for the 12-h PK test visit. Subjects will undergo clinic visit procedures including: a review of inclusion/exclusion criteria, concomitant medication/supplement use, body weight, and vital signs assessment. Adverse events (AE) will be assessed and subjects will be queried about study instructions compliance. Additionally, the 24-h Diet Record will be collected and reviewed. A fasting capillary blood glucose will be assessed to confirm fasting status. Eligible subjects will be enrolled and will begin the PK test with the insertion of an intravenous catheter at least 5 min prior to the first blood sampling time. In order to maintain patency of the intravenous catheter, the catheter will be flushed with normal saline solution at least hourly. Blood samples will be drawn by venipuncture if the catheter fails. Blood samples will be obtained at $t = -0.25 \text{ h} \pm 10 \text{ min}$ for the PK analysis of serum strontium, where t = 0 h is the time of study product consumption. Additional blood samples will be collected at all timepoints for backup. Subjects will consume the study product in its entirety within 10 min at t = 0 h. The study product will be dissolved with 100 mL of distilled water with an additional 100 mL of distilled water consumed immediately following. No food will be ingested for the subsequent 2-h period, but ad libitum water consumption will be allowed for the remainder of the visit following study product consumption. Water consumption will be recorded at the subsequent test visits. Blood samples will be obtained for the PK analysis of serum strontium at t = 1 and $2 h \pm 5$ min, where t = 0 h is the start of study product consumption. Subjects will be administered a standard breakfast immediately following the t = 2 h blood draw. Subjects will consume the breakfast meal in its entirety within 30 min.

Blood samples will be obtained via the indwelling venous catheter or venipuncture at t=3,4,5,6, and $8 \text{ h} \pm 5 \text{ min}$, where t=0 h is the start of study product consumption, for the PK analysis of serum strontium. Subjects will be administered a standard lunch (immediately following the t=6 h blood draw), a standard snack (immediately following the t=8 h blood draw) and a standard dinner (at t=10 h). Subjects will consume the meals/snack in their entirety within 30 min. Following the final blood draw at $t=12 \text{ h} \pm 5 \text{ min}$, AEs will be assessed. Subjects will be dispensed a blank/new 24-h Diet Record to record all food and beverage consumed the day prior to Visit 3 (day 7); as well as a copy of the completed 24-h Diet Record (from day -1) with instructions to replicate the same food and beverage intake as closely as possible the day prior to the subsequent visit. Study instructions will also be provided [(i.e., fasting compliance (10-14 h, water only) and avoidance of alcohol 3 d prior to the subsequent test visits].

At Visits 3 and 4 (days 7 and 14), subjects will return to the clinic for clinic visit procedures (i.e., vital signs; body weight; review inclusion and exclusion criteria for relevant changes, and concomitant medication/supplement use review). AEs will be

assessed and subjects will be queried about study instructions compliance. The 24-h Diet Record will be collected and study staff will review the 24-h Diet Record to compare food and beverage consumption to the day -1 recall for consistency. If the subject's food intake is not consistent from the 24-h Diet Record reviewed at Visit 2 (day 0), the study staff should contact the Project Manager before continuing the visit as the test visit may require rescheduling. Subjects will then crossover to the next sequential dose of study product [medium dose at Visit 3 (day 7) and high dose at Visit 4 (day 14)] and repeat the PK test described above for Visit 2.

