 11 A copy of the 24-h Diet Record captured the day prior to Visit 2 (day 0) will be given to subjects with instructions to replicate the food and beverage selections to the best of their abilities 12 Subjects will arrive at the clinic following an overnight fast (10-14 h). Blood samples will be obtained for the PK analysis of serum strontium at t = -0.25 h \pm 10 min and 1, 2, 3, 4, 5, 6, 8, and 12 h (\pm 5 min) where t = 0 h is the time of study product consumption. The study product will be dissolved with 100 mL of distilled water with an additional 100 mL of distilled water consumed immediately following. No food will be ingested for the subsequent 2-h period, but *ad libitum* water consumption will be allowed for the remainder of visit following study product consumption. Water consumption will be recorded at the subsequent test visits. A self-selected standard breakfast (immediately following the t = 2 h blood draw), lunch (immediately following the t = 6 h blood draw), snack (immediately following the t = 8 h blood draw), and dinner (at t = 10 h) will be administered. The study product at Visits 3 and 4 (days 7 and 14) will be administered within t = 0 h time established at Visit 2 and the meals will be replicated (Appendix 4).

¹³Backup aliquots of serum will be collected and stored for each timepoint.

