5.5 Study Products

5.5.1 Description

- Low dose (170 mg Sr) strontium *L*-lactate
- Medium dose (340 mg Sr) strontium L -lactate
- High dose (680 mg Sr) strontium L -lactate

The study product will be provided as a dry powder packaged in individual vials. The study product will be prepared for consumption by dissolving the dry powder in the vial by adding 10 mL of distilled water and stirring the mixture. This liquid mixture will then be poured into an administration cup. An additional 10 mL of distilled water will be used to rinse the remaining study product into the administration cup. The remaining 80 mL of distilled water will be added directly into the administration cup. Following subject consumption of the 100 mL distilled water (with dissolved study product powder), another 100 mL will be added into the administration cup, swirled, and consumed by the subject. Study product information may be found in Appendix 5.

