5.6.2 Laboratory Measurements

The procedures for all clinical laboratory measurements will be outlined in a laboratory instruction sheet. **Lab**oratory parameters that are missing or have not been obtained must be entered in the eCRF as "not done."

The FDA-approved glucometer, with test strips from the same lot, will be used for determination of the in-clinic (Biofortis Clinical Research, Addison, IL) fasting capillary blood glucose (mmol/L) at Visits 1, 2, 3, and 4 (days -7, 0, 7, and 14) to ensure adequate fasting (10-14 h). Visits may be rescheduled for non-compliance, in the judgment of the Clinical Investigator.

The following will be performed as a part of the fasting (10-14 h) chemistry profile at Visit 1 (day -7): glucose, sodium, potassium, chloride, carbon dioxide, BUN, creatinine, calcium, osmolality, AST, ALT, ALP, total bilirubin, total protein, and albumin. Analytes will be assessed by Elmhurst Memorial Reference Laboratory (Elmhurst, IL).

The following will be performed as part of the fasting (10-14 h) hematology measurements at Visit 1 (day -14): WBC, RBC, hemoglobin concentration, hematocrit (as volume percent), MCV, MCH, MCHC, neutrophils, lymphocytes, monocytes, eosinophils, basophils and platelet count. Analytes will be assessed by Elmhurst Memorial Reference Laboratory (Elmhurst, IL).

Blood samples for the PK analysis of serum strontium will be collected at Visits 2, 3 and 4 (days 0, 7, and 14) at t = -0.25 h (\pm 10 min) and $t = 1, 2, 3, 4, 5, 6, 8, 10, and 12 h (<math>\pm$ 5 min), where t = 0 h is the start of study product consumption. Analytes will be assessed by NMS Labs (Willow Grove, PA). Additional samples will be stored as backup in the event the original sample is not viable.

An in-clinic urine pregnancy test will be performed on all women <60 years of age at Visit 1 (day -7).

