6.1 Outcome Variables

The outcome variables will include the following parameters for serum strontium at all three doses:

- Incremental area under the curve (iAUC) for serum strontium from pre-product consumption (t = -0.25 h) to 12 h (iAUC-_{0.25-12h})
- iAUC for serum strontium from pre-product consumption (t = -0.25 h) to infinity (AUC_{0- ∞})
- Maximum plasma concentration (Cmax)
- Time to Cmax (Tmax)
- Rate of elimination (λ_z)
- Half life $(t_{1/2})$
- Estimated fraction of the dose which is absorbed

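### With no draw between dosing and 1 h, the schedule cannot detect or rule out a serum strontium peak in the first hour

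*Combined protocol and SAP*

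**What the plan says.** **Sampling times.** After the pre-dose draw at -0.25 h, Section 5.2 continues with "Blood samples will be obtained for the PK analysis of serum strontium at t = 1 and" 2 h, each ± 5 min, and then goes on to 12 h. Section 5.6.6 and its test-day table agree. Flowchart footnote 12 lists "1, 2, 3, 4, 5, 6, 8, and 12 h". Section 5.6.2 lists "1, 2, 3, 4, 5, 6, 8, 10, and 12 h". The lists disagree about a 10-h draw, which needs separate reconciliation, but all of them start at 1 h.

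**Dosing.** Section 5.5.1 says "The study product will be prepared for consumption by dissolving the dry powder in the vial". Section 5.2 adds "The study product will be dissolved with 100 mL of distilled water with an additional 100 mL of distilled water consumed immediately following" and "Subjects will consume the study product in its entirety within 10 min at t = 0 h". Subjects have fasted 10-14 h and eat nothing for a further 2 h.

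**Prior knowledge.** The Background states that "no clinical trials have been conducted with Stratum Plus". No section gives an expected Tmax, an absorption rate, a half-life or a reason for the chosen times.

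**Outcomes.** Section 3 names PK information as the only objective. Section 6.1 lists iAUC from -0.25 to 12 h, Cmax, Tmax, the elimination rate and half-life among the outcomes at each dose.

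**The concern.** A solution taken on an empty stomach needs no disintegration and meets no food, so a peak inside the first hour is plausible. The schedule has nothing there to see it with.

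Three consequences hold whatever the absorption rate. The earliest Tmax that can be reported is the first draw. The first 1.25 h of iAUC is a single trapezoid. A profile whose highest value is at 1 h cannot be told apart from one that peaked earlier and is already falling.

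If the peak does come early, the errors all go one way: Cmax and iAUC low, Tmax late. Averaging over 6 to 10 subjects does not remove a one-directional error. Nor can it be recovered afterwards, because Section 6.7 rules out imputation and footnote 13 provides backup serum only at the scheduled timepoints.

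**Working it through.** The documents state no bias or precision figure, so there is nothing to reproduce. The check compares assumed noise-free curves, with pre-dose strontium subtracted, with what the schedule would record.

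**Inputs from the documents.** Draws at -0.25, 1, 2, 3, 4, 5, 6, 8 and 12 h; iAUC from -0.25 to 12 h.

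**Assumptions.** Curve shape, absorption rate ka and elimination rate ke. The linear trapezoid is also assumed.

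**Earliest Tmax.** 60 min - 5 min = 55 min.

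**One curve in full.** One compartment, unit scale: C(t) = ka/(ka - ke) × [exp(-ke t) - exp(-ka t)], with ka = 5 and ke = 0.30 per h.

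- True Tmax = ln(5/0.30)/(5 - 0.30) = 2.813/4.7 = 0.60 h. True Cmax = 0.8356.
- Largest sampled value: C(1) = 0.7809. Cmax error = 0.7809/0.8356 - 1 = -6.5%; Tmax is recorded as 1 h.
- True area, 0 to 12 h = 3.236. The first trapezoid is 1.25 × 0.7809/2 = 0.488 and the other seven sum to 2.576. Total 3.064, error -5.3%.
- Starting the area at 0 h instead would make the first trapezoid 0.390 and the error -8.3%. The plan starts at -0.25 h, so -5.3% applies.
- With a 0.5-h draw, C(0.5) = 0.8283. Cmax error = 0.8283/0.8356 - 1 = -0.9%. The area up to 1 h becomes 0.75 × 0.8283/2 + 0.5 × (0.8283 + 0.7809)/2 = 0.311 + 0.402 = 0.713. Total 3.289, error +1.6%.

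**One-compartment range, ka 0.3 to 5 and ke 0.02 to 0.30 per h, true Tmax below 0.75 h.** Cmax is 1.9 to 6.5% low and iAUC 3.0 to 5.3% low. The low ends come from the curve nearest the 0.75-h boundary (ka 5, ke 0.15, Tmax 0.72 h). Without it they are about 3% and 4%.

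**One compartment, ka solved for each assumed Tmax.** Errors in %; half-lives of 6 and 12 h fall between those shown.

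| True Tmax (h) | Half-life (h) | Cmax now | iAUC now | Cmax with 0.5 h | iAUC with 0.5 h |
|---|---|---|---|---|---|
| 0.25 | 2 | -21.1 | -10.6 | -6.3 | -1.2 |
| 0.25 | 60 | -0.8 | -3.1 | -0.3 | -0.8 |
| 0.5 | 2 | -11.1 | -7.3 | 0.0 | +1.3 |
| 0.5 | 60 | -0.5 | -2.7 | 0.0 | -0.5 |
| 0.75 | 2 | -2.7 | -4.0 | -2.7 | +2.2 |
| 0.75 | 60 | -0.2 | -2.4 | -0.2 | -0.2 |
| 1 | 2 | 0.0 | -1.7 | 0.0 | +2.2 |
| 1 | 60 | 0.0 | -2.0 | 0.0 | 0.0 |
| 2 | 2 | 0.0 | +1.2 | 0.0 | +1.7 |
| 2 | 60 | 0.0 | -0.8 | 0.0 | +0.3 |

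The 0.25-h and 0.5-h rows need ka from about 6 to 32 per h, faster than the range above.

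**Two compartments, true Tmax below 0.75 h.**

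- ka 1 to 8 per h, distribution half-life 0.5 to 1 h, fast share 0.5 to 0.8, terminal half-life 24 h: Cmax is 3.4 to 40.3% low and iAUC 2.8 to 10.6% low.
- ka 0.5 to 5, k12 0.3 to 1.5, k21 0.2 to 0.5, k10 0.05 to 0.20 per h: the worst curves reach about 47% of Cmax and 15% of iAUC.
- With a 0.5-h draw added, the worst Cmax errors fall to about 10% and 7.5% respectively, and iAUC stays within about 2%.

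**Peaks at 1 h or later.** A peak between two whole-hour draws can still read up to about 5% low (for example 4.7% at a true Tmax of 1.41 h). That comes from the spacing between 1 and 2 h, and a 0.5-h draw does not change it.

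**The case against.** The strongest objection is that nothing shows the peak is early. Dissolving the product removes disintegration time but does not establish a Tmax under 1 h, and drinking may take up to 10 min. The absence of earlier trials leaves a later peak just as possible. This stands. A reader might infer that an early peak is being missed and that Cmax, Tmax and iAUC are biased as a matter of fact; the documents do not support that, because they give no absorption rate or half-life.

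A reader might also take a 40% loss of Cmax as typical. It comes only from assumed two-compartment curves with fast absorption and rapid distribution, and the documents do not say that strontium L-lactate behaves that way.

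A third tempting inference is that the 5-h draw adds little and could pay for an earlier one. That is not shown. If the true peak is near 5 h, dropping the draw makes Cmax read 0.4 to 1.6% low and puts Tmax at 6 h. The effect on the elimination rate and half-life, both listed outcomes, was not tested.

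Finally, the study is descriptive (Section 6.5), enrols 10 subjects with no formal sample-size calculation (Section 6.2), and uses one schedule at all doses. Under linear kinetics a proportional error largely cancels between doses. That softens the point for dose comparisons, but not for the absolute Cmax, Tmax and iAUC reported at each dose.

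**Conclusion.** The concern holds in conditional form: the schedule can neither detect nor exclude a first-hour peak, and it gives no reason for starting at 1 h. The floor on Tmax and the single 1.25-h trapezoid are certain. The size of any error depends on assumed kinetics: a few per cent of Cmax and iAUC in ordinary one-compartment curves, more with faster absorption and short half-lives, and large only under marked early distribution. With a 60-h half-life the Cmax loss is negligible but Tmax is still recorded late. If the peak is at 1 h or later, the early gap does little harm. The change is worth making because PK description is the study's whole purpose, the gap cannot be repaired after the fact, and the remedy is small. The calculations assume noise-free profiles, exact draw times and no absorption lag.

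**What to change.** Add a serum strontium draw at t = 0.5 h (± 5 min), with its backup aliquot, at Visits 2, 3 and 4. Enter it in Section 5.2, flowchart footnote 12, Section 5.6.2, Section 5.6.6 and the test-day schedule. Keep the 5-h draw. State in Section 6.5 that any profile whose Cmax falls at the first post-dose sample will be flagged, since an earlier peak then remains possible.

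The cost is a protocol amendment and one more catheter draw and assay per visit: 3 per subject, or 3 × 10 = 30 if all 10 enrolled subjects complete. The catheter is already in place and the subject in clinic. The remaining drawbacks are a trapezoidal iAUC that may read slightly high (up to about 2%) for some curves, and a very early, sharp peak that could still be understated.

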5.3 Flowchart

			Test Days	
	Screening	Low Dose	Medium Dose	High Dose
Visit ¹	1	2	3	4
Days	-7	0	7	14
Informed Consent/HIPAA ²	X			
Clinic Visit ³	X	X	X	X
Medical History	X			
Chemistry Profile ⁴	X			
Hematology Panel ⁵	X			
In-clinic Urine Pregnancy Test ⁶	X			
Vein Access Scale Assessment ⁷	X			
Study Instructions/Query ⁸	X	X	X	X
Enrollment		X		
Capillary Glucose ⁹	X	X	X	X
Dispense 24-h Diet Record ¹⁰	X	X	X	
Collect/Review/Copy 24-h Diet Record ¹¹		X	X	X
Pharmacokinetic Test ¹²		X	X	X
Backup Blood Samples ¹³		X	X	X
Adverse Event Assessment ¹⁴		X	Х	X

Footnotes:

¹ A period up to 21 d will be allowed between Visits 1 and 2 (days -7 to 0) and the washout period between Visits 2 and 3 (days 0 and 7) and Visits 3 and 4 (days 7 and 14) will be 6-13 d.

³Clinic visit procedures include measurement of height (Visit 1 only), body weight, BMI (first visit only), vital signs, and where appropriate, a review of inclusion/exclusion criteria (for eligibility at Visit 1 and for potential protocol deviations at subsequent visits), and concomitant medication/supplement use.

⁴The following will be performed as part of the fasting (10-14 h) chemistry profile: albumin, alkaline phosphatase, total bilirubin, direct bilirubin, calcium, chloride, creatinine, blood urea

² Health Insurance Portability and Accountability Act (HIPAA) for disclosure of protected health information. Signed document authorizes the use and disclosure of the subject's Protected Health Information by the Investigator and by those persons who need that information for the purposes of the study.

nitrogen (BUN), potassium, aspartate aminotransferase (AST), alanine aminotransferase (ALT), sodium, total protein, carbon dioxide (CO₂), osmolality, and glucose.

⁵The following will be performed as part of the fasting (10-14 h) hematology panel: white blood cell count (WBC), red blood cell count (RBC), hemoglobin concentration, hematocrit (as volume percent), mean cell volume (MCV), mean cell hemoglobin (MCH), mean cell hemoglobin concentration (MCHC), neutrophils, lymphocytes, monocytes, eosinophils, basophils and platelet count.

⁷Appendix 2.

¹⁰Subjects will complete a 24-h Diet Record identifying all food and beverages consumed the day prior to Visit 2 (day 0; Appendix 3). A clean copy of the 24-h Diet Record will also be provided with instructions for subjects to complete the record the day prior to Visits 3 and 4.

 11 A copy of the 24-h Diet Record captured the day prior to Visit 2 (day 0) will be given to subjects with instructions to replicate the food and beverage selections to the best of their abilities 12 Subjects will arrive at the clinic following an overnight fast (10-14 h). Blood samples will be obtained for the PK analysis of serum strontium at t = -0.25 h \pm 10 min and 1, 2, 3, 4, 5, 6, 8, and 12 h (\pm 5 min) where t = 0 h is the time of study product consumption. The study product will be dissolved with 100 mL of distilled water with an additional 100 mL of distilled water consumed immediately following. No food will be ingested for the subsequent 2-h period, but *ad libitum* water consumption will be allowed for the remainder of visit following study product consumption. Water consumption will be recorded at the subsequent test visits. A self-selected standard breakfast (immediately following the t = 2 h blood draw), lunch (immediately following the t = 6 h blood draw), snack (immediately following the t = 8 h blood draw), and dinner (at t = 10 h) will be administered. The study product at Visits 3 and 4 (days 7 and 14) will be administered within t = 0 h time established at Visit 2 and the meals will be replicated (Appendix 4).

¹³Backup aliquots of serum will be collected and stored for each timepoint.

